### **7.2 Hypotheses Statements:**

Not applicable. The study is hypothesis generating only.

**7.3 Interim Analyses.** No interim analyses are planned.

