#### *Treatment Opportunities:*

The primary benefit of early anticoagulation is a reduction in early recurrent embolic events and therefore improved outcomes. Dabigatran offers the possibility of rapid therapeutic anticoagulation in this setting, a significant benefit over the days to weeks required to achieve a therapeutic INR with warfarin. The complexities associated with initiating warfarin therapy result in a significant treatment gap. Data from the Registry of the Canadian Stroke Network indicate that nearly 50% of patients with cardioembolic stroke are not anticoagulated one year after their index event. Early treatment initiation is expected to result in improved rates of anticoagulation following stroke and greater adherence to therapy. The acute stroke period, when patients are cared for in stroke units, by specialized physicians

represents an opportunity to optimize therapy, including lifelong anticoagulation. If it can be demonstrated that dabigatran can be safely administered early after stroke, as warfarin is used currently, it may ultimately result in higher rates of long-term anticoagulation and consequently a reduction in stroke rates. The current wording in the product monograph stipulating a delay in initiation of dabigatran will result in continued use of warfarin in patients for whom Dabigatran would have greater safety and efficacy.

Given the equipoise and variable practice patterns amongst CSC physicians, the safety of dabigatran after stroke can be effectively addressed using a prospective single arm study design. We have sufficient variability and ischemic stroke patient volume nation-wide to ensure a broad based sample with respect to stroke severity and timing of dabigatran initiation. We have therefore designed a registry of dabigatran treatment following ischemic stroke/TIA. A unique feature of the CPASS registry is the central collection and reading of all imaging data. This will provide invaluable information related to both the nature and predictors of any HT associated with early dabigatran use. The CSC has successfully conducted a phase IV registry of this nature, including central image reading and analysis, in the past (Canadian Alteplase for Acute Stroke Effectiveness Study).

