## **2. Canadian Pradox Acute Stroke/TIA Safety Study (CPASS) Rationale and Objectives**

### ***2.1 Rationale***

Ideally, anticoagulation should be started as soon as possible following a stroke/TIA in patients with new or previously diagnosed atrial fibrillation. This prevents early recurrent events and also ensures long-term secondary prevention strategies are implemented at the point of maximum medical contact, which is always at the time of the acute event. The rate of hemorrhagic complications associated with older anticoagulants has never been well characterized, but is recognized as a genuine risk that must be considered and generally delays anticoagulation. As described above, intracranial hemorrhagic complication rates in dabigatran-treated patients are markedly lower than those associated with older anticoagulants. Thus, dabigatran is hypothesized to be an ideal drug for early anticoagulation after acute stroke/TIA.

Although aggressive antithrombotic therapy has been shown to reduce the number of new ischemic events following stroke/TIA, this has always been offset by an increase in the risk of hemorrhagic complications. Dabigatran appears to be much safer with respect to intracranial bleeding and therefore offers a unique treatment opportunity in these high-risk patients. A registry will provide critical reassurance to stroke clinicians concerned about precipitating hemorrhagic transformation. If it can be

demonstrated to be safe, early treatment with dabigatran can be recommended, which may lead to lower rates of cardioembolic stroke recurrence. In addition, this will facilitate optimal treatment of patients who require long-term anticoagulation after ischemic stroke.

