## **3. Canadian Pradox Acute Stroke/TIA Safety Study (CPASS) Design**

**3.1 Study Aim and Design:** The primary aim of the CPASS registry is to demonstrate the safety of early anticoagulation with dabigatran following cardioembolic stroke. CPASS is a prospective open label single arm observational study. Safety will be established by demonstrating low rates of hemorrhage in this setting.

**3.1.1 Administrative Structure:** CPASS is a Canadian Stroke Consortium led study. The study coordinating centre is at the University of Alberta. Case report forms and data monitoring will be completed electronically, using an online EDC system. All imaging data will be read centrally at the Stroke Imaging Laboratory at the University of Alberta.

**3.2 Study Design Considerations:** A randomized controlled design was considered (dabigatran versus warfarin). This is considered impractical for a number of reasons. Novel oral anticoagulants are recommended as first line agents for stroke prevention in AF patients by the Canadian Cardiovascular Society. These agents are associated with improved safety with respect to bleeding complications. This makes randomization of a patient to warfarin who would otherwise be prescribed dabigatran somewhat ethically dubious. In addition, a randomized design would necessitate a very large study, which would not be completed in a reasonable period of time. A registry design allows us to address the question of safety in a systematic fashion. A safety threshold has been defined for any anticoagulant use early after stroke, based on the rates of warfarin-associated intracranial hemorrhage, which have been reported to be 0.5 to 2.5 per 100 patient years. The registry design therefore permits determination of whether or not dabigatran is within this threshold. Finally, the systematic collection of clinical and imaging data will allow us to determine any risk factors for hemorrhagic transformation associated with early anticoagulation.

**3.3 Selection of Population.** A log of all patients included in the study (consent obtained) will be maintained at the trial coordinating centre, irrespective of whether they are treated or not. Only patients actually treated with dabigatran will be followed in the registry. Basic patient demographics, ethnicity, stroke severity (NIHSS), medications, including previous warfarin use, previous stroke/TIA, other co-

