## **7. Statistical Methods and Sample Size**

**7.1 Statistical Analysis and Sample Size Considerations:** The registry will include 500 patients. This sample size is considered adequate to ensure inclusion of a significant number of patients treated at a range of time points within the post-stroke period. The primary analysis will be done on an Intention

To Treat basis. We will also complete a sensitivity analysis on individuals who discontinued dabigatran treatment and/or switched to other antithrombotic agents. Based on the inclusion/exclusion criteria, there will not be any individuals taking dabigatran concomitantly with other antithrombotic drugs.

The primary and secondary outcomes will be defined with descriptive statistics. The rate of PH2 (and all other forms of hemorrhagic transformation) will be defined as a ratio (%) of the total number of patients enrolled in the study (ITT analysis).

The primary stratification variable is warfarin use prior to the TIA/minor stroke. The secondary strata are 1. Dabigatran dose (150 mg BID versus 110 mg BID) and 2. Time to initiation of therapy (0-2 days, 3-7 days and > 7 days). All results including baseline patient characteristics will be stratified by use of warfarin prior to the event and by the dabigatran dose after the event as described in **appendices 2-4**.

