**Limitations.** There are recognized limitations to this study. The eligibility criteria are consistent with a low risk population, and the results of this study will not be generalizable to other, higher risk stroke/TIA populations. Even in the population of TIA and minor stroke patients, the time between symptom onset and treatment initiation may vary with the severity of the clinical presentation. Although it is not our intention, clinicians may be more likely to initiate therapy earlier in patients with complete resolution of all neurological deficits. Only dabigatran treated patients will be included in this registry. Unintended selection bias may also arise from survival bias over the time from incident stroke/TIA to time of dabigatran treatment and start of follow-up. Finally this is a small (500) single arm study with a relatively short (30 day) follow-up period. This short time period will permit assessment of the most important safety variable (hemorrhagic transformation rates). It will also minimize loss to follow-up. Although functional outcome is generally assessed at 90 days, this pilot study is too small to adequately assess that endpoint.

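### The protocol says it will demonstrate safety and test a warfarin-based threshold, but section 7 plans only a percentage, and 500 patients over 30 days cannot show that the threshold is met

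*Combined protocol and SAP*

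**What the plan says.** The synopsis and section 3.1 state the aim in confirmatory terms: "The primary aim of the CPASS registry is to demonstrate the safety of early anticoagulation with dabigatran following cardioembolic stroke". Both continue: "Safety will be established by demonstrating low rates of hemorrhage in this setting". Objective 1 in section 2.2 also uses the verb demonstrate.

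Section 3.2 adds a criterion. It says that a safety threshold exists, based on reported warfarin-associated intracranial hemorrhage rates of 0.5 to 2.5 per 100 patient-years, and that the registry design allows a judgement on whether dabigatran falls within it. Section 2.3 gives two further figures: 1.7% symptomatic hemorrhagic transformation with heparin within one week, and 0.6% expected with dabigatran.

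The statistical section takes another line. Section 7.2 reads "Not applicable. The study is hypothesis generating only". Section 7.1 says "The primary and secondary outcomes will be defined with descriptive statistics" and expresses each hemorrhage rate as a percentage of all enrolled patients. It names no confidence interval, margin or decision rule, and it does not mention the section 3.2 threshold. The synopsis says there are too few data on which to base a sample size.

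On population, eligibility is TIA or ischemic stroke with NIHSS 3 or less. Section 1.1 (Treatment Opportunities) says patient volume will "ensure a broad based sample with respect to stroke severity and timing of dabigatran initiation", while the Limitations paragraph of section 7.1 says "the results of this study will not be generalizable to other, higher risk stroke/TIA populations".

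**The concern.** A study that generates hypotheses and reports percentages can estimate a rate. It cannot establish safety, and it cannot place a rate inside a threshold unless there is a rule linking the data to that threshold. The front of the protocol promises both, and section 7 supplies the means for neither.

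With about three events expected, most of the information lies in the interval rather than the point estimate. If the plan is followed as written, a bare 0.6% could be reported as a low rate, and therefore as safety established, without the reader seeing which higher rates remain compatible with the data. The stake is practical: section 2.1 says that, if safety can be demonstrated, "early treatment with dabigatran can be recommended".

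**Working it through.** **Inputs.** N = 500 (section 7.1); outcome period 30 days (section 6.2.2); threshold 0.5 to 2.5 per 100 patient-years (section 3.2); heparin rate 1.7%, ratio 1/3 and expected rate 0.6% (section 2.3). Complete 30-day follow-up is assumed.

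**1. The plan's own figure.** 1.7% × 1/3 = 0.567%, which rounds to the stated 0.6%, or 500 × 0.006 = 3 events. The arithmetic reproduces, although the 1/3 is a ratio against warfarin applied to a heparin rate. N = 500 cannot be checked, because no precision target, margin, alpha or power is given.

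**2. The threshold on the 30-day scale.** At a constant rate, the 30-day percentage is the rate per 100 patient-years × 30/365.25.
- Lower end: 0.5 × 30/365.25 = 0.041%, or 0.2 events in 500.
- Upper end: 2.5 × 30/365.25 = 0.205%, or 1.0 event in 500.
- Expected rate, converted back: 0.6 × 365.25/30 = 7.3 per 100 patient-years. 7.3/2.5 = 2.9, so the protocol expects about three times the top of its own threshold.

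**3. What 500 patients can show.** Exposure is 500 × 30/365.25 = 41.1 patient-years. Exact two-sided 95% limits are Clopper-Pearson: lower = Beta(0.025; x, n−x+1), upper = Beta(0.975; x+1, n−x).

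| Events | Rate | Per 100 patient-years | Exact two-sided 95% CI | One-sided 95% upper limit |
|---|---|---|---|---|
| 0 | 0% | 0 | 0 to 0.74% | 0.60% |
| 1 | 0.2% | 2.44 | 0.005 to 1.11% | 0.95% |
| 2 | 0.4% | 4.87 | 0.05 to 1.44% | 1.25% |
| 3 | 0.6% | 7.31 | 0.12 to 1.74% | 1.54% |
| 4 | 0.8% | 9.74 | 0.22 to 2.04% | 1.82% |

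**4. Against the threshold.** The best possible result is 0/500. Its one-sided 95% upper limit is 1 − 0.05^(1/500) = 0.60%; the exact Poisson limit is 7.3 per 100 patient-years. Both are about three times the top end (0.205%, or 2.5). An upper limit below 0.205% with no events would need ln(0.05)/ln(1 − 0.00205) = 1,458 patients. Zero is also the best possible count of any intracranial hemorrhage, so the conclusion does not depend on which endpoint is counted. The data could show the reverse: at 4 events the lower two-sided limit (0.22%, or 2.65 per 100 patient-years) lies above the top end.

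**5. Against the heparin rate.** The expected 3/500 has an upper limit of 1.74%, above 1.7%. With a two-sided 95% interval, 2 events or fewer are needed to exclude 1.7%. If the true rate is 0.6%, the chance of that is 42.3%.

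**The case against.** The strongest reply is that the protocol does put figures on low. A reader might infer that any result could be reported as proof of safety; the documents do not support that. Section 3.2 names a threshold and section 2.3 names 0.6% and 1.7%. Read literally as a point estimate, the threshold is demanding: only 0 or 1 event in 500 falls within it, and if the true rate is 0.6% the chance of that is 19.8%. This stands. The fault is that the stated criterion is not usable: it is a range, it is per patient-year, it concerns intracranial hemorrhage rather than PH2 with NIHSS worsening of 4 or more, and section 7 does not take it up.

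Second, section 2.1 might be read as already moving to a treatment recommendation. It does not; the sentence is conditional on safety being demonstrated.

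Third, the aim's reference to cardioembolic stroke might be read as a claim about all severities. The synopsis indication, objective 1 and the Limitations paragraph already confine the study to TIA and minor stroke. What remains is loose wording in the synopsis aim, section 3.1 and section 1.1.

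Fourth, descriptive statistics do not rule out a confidence interval. That is true, but none is specified.

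Finally, the 1.7% comparison depends on the interval chosen. With a one-sided 95% limit, 3/500 gives 1.54% and would exclude it. The documents do not set 1.7% as a limit, and section 1.1 describes it as an increase in hemorrhagic transformation while section 2.3 calls it the risk. This is a reason to fix the interval in advance and to treat 1.7% as a reference figure only.

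**Conclusion.** The point holds. The wording about demonstrating and establishing safety conflicts with section 7.2 and has no matching analysis in section 7.1. The section 3.2 claim is unattainable in the direction that matters: 500 patients over 30 days can show that the threshold is exceeded, but never with 95% confidence that it is met. Even zero events leaves an upper limit about three times its top end, and the protocol's own expectation sits at that same multiple. The expected result would not exclude 1.7% with a two-sided 95% interval.

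This rests on complete follow-up, with fewer patient-years making the limits wider, and on a constant rate when converting patient-years to 30 days. It also takes the 500 as the denominator throughout. Section 7.1 divides by all enrolled patients while section 3.3 follows only those treated, so that needs to be made consistent. The population wording is a minor editorial matter.

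**What to change.** 1. In the synopsis, 2.2 and 3.1, restate the aim as estimating, with an exact 95% confidence interval, the 30-day symptomatic hemorrhagic transformation rate in AF patients with TIA or minor stroke (NIHSS 3 or less) started on dabigatran within 14 days.
2. Delete "Safety will be established by demonstrating low rates of hemorrhage in this setting" from the synopsis and 3.1.
3. In 7.1, report each rate with its exact two-sided 95% interval, and have the conclusion say which rates the upper limit does and does not exclude, including the 1.7% and 0.6% of section 2.3. The team should know beforehand that no result in 500 excludes 0.6% on this interval, since 0/500 reaches 0.74%.
4. In 3.2, remove the statement that the design can settle whether dabigatran is within the threshold, or say that 500 patients over 30 days cannot show this.
5. As a consistency edit, limit the cardioembolic stroke wording in the synopsis aim and 3.1 to TIA and minor stroke, and drop the broad-severity wording in 1.1.

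The cost is wording and a trivial added calculation, with no new patients, procedures or data. The claim becomes narrower, in line with what 7.2 and the Limitations paragraph already concede.

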## **8. Informed Consent, Data Protection, Study Records**

The study will be carried out in compliance with the protocol, the principles laid down in the Declaration of Helsinki, in accordance with the ICH Harmonized Tripartite Guideline for Good Clinical Practice (GCP) and relevant BI Standard Operating Procedures (SOPs). Standard medical care (prophylactic, diagnostic and therapeutic procedures) remains the responsibility of the treating physician of the patient.

The investigator should inform Boehringer-Ingelheim immediately of any urgent safety measures taken to protect the study subjects against any immediate hazard, and also of any serious breaches of the protocol/ICH GCP.

The rights of the investigator and of Boehringer-Ingelheim with regard to publication of the results of the study are described in the investigator-initiated study contract. As a general rule, no study results should be published prior to finalization of the study report.

**8.1 Source Documents.** Source documents provide evidence for the existence of the patient and substantiate the integrity of the data collected. Source documents are filed at the investigator site. Data reported in the CRF that are transcribed from source documents must be consistent with the source documents or the discrepancies must be explained. The investigator may need to request previous medical records or transfer records, pending on the trial; also current medical records must be available.

## Appendix 1: Baseline patient characteristics to be collected in case report form.

Variable	Stratification (if applicable)	
Sex	M	F
Age	>80	<80
Prior TIA	Y	N
Prior Stroke	Y	N
Carotid Stenosis	Y	N
Carotid Endarterectomy	Y	N
Carotid Stent	Y	N
Prior STEMI	Y	N
Prior NSTEMI	Y	N
CABG	Y	N
Coronary Stent	Y	N
Chronic Renal Failure	eGFR <60 >50 ml/min	eGFR >30 <50 ml/min
Diabetes	Y	N
HbA1c	>7%	<7%
Hypertension	Y	N
Systolic BP at recruitment	>140 mmHg	<140 mmHg
Diastolic BP at recruitment	>90 mmHg	<90 mmHg
CHF history	Y	N
Dementia history	Y	N
Medications	List	
Current Smoker		
Ex-smoker		
CHADS2 (0-6)		
CHADS-VASc (0-6)		
HAS-BLED (0-6)		
Alcohol/drug abuse	Y	N
History of PE/DVT	Y	N
Impaired liver function	Y	N
Prior intracranial hemorrhage	Y	N
Prior GI/GU hemorrhage	Y	N
Prior other hemorrhage	Y	N
Prior cerebral aneurysm	Y	N
peripheral artery disease (PAD), aortic plaque	Y	N
time since first AF diagnosis	Y	N
Previous cardioversion	Y	N
Ethnicity		
Heart rate		
Weight/height/BMI		

Appendix 2: Patient characteristics stratified by prior stroke treatment and dabigatran dose post TIA/stroke.

	Treatment prior to TIA/stroke				
	VKA naive		VKA		
	Dabigatran dose post TIA/stroke				
Baseline	110 mg	150 mg	110 mg	150 mg	P value (VKA naive vs. VKA)
Age, Sex					
Prior TIA					
Index event					
TIA/stroke					
Treatment					
Lysis, surgery					
Dabigatran treatment initiation after TIA/stroke					
0-2 days					
0					
1					
2					
3-7 days					

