**Statistical Analyses:**

The primary outcome will be occurrence of PH2 at 30 days. Secondary outcomes will be ischemic stroke, any intracerebral hemorrhage, MI and death. In addition we will compare the rate of hemorrhagic transformation in patients started on dabigatran within 7 days of stroke/TIA versus those started  $>7$  days after symptom onset.

Descriptive statistics will be used to describe all outcomes (see protocol section 7.1).

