morbidities, particularly hypertension, diabetes, hypercholesterolemia and ischemic heart disease, CHADS-Vasc, HAS-BLED, history of gastrointestinal or other hemorrhage will all be recorded (**Appendix 1**).

**3.3.1 Patients.** Male and female patients with acute TIA or ischemic stroke will be recruited from the Emergency Departments and stroke units at CSC investigator sites. All patients will have documented evidence of atrial fibrillation (permanent or paroxysmal). Informed consent will be obtained from patients or surrogate decision makers prior to enrolment in all cases.

**3.3.2 Inclusion Criteria.** All patients will be 18 years or older. Eligible patients will have ischemic stroke (NIHSS score  $\leq 3$ ) or TIA (complete resolution of focal neurological deficits within 24 hours) and atrial fibrillation (paroxysmal or persistent). The decision to treat with dabigatran and the timing of the first dose will be determined by the attending physician, independent of the registry. In cases where stroke onset time cannot be established, it will be considered to be the time when the patient was last known to be well. All patients will have a CT scan or MRI, with findings consistent with an ischemic etiology of symptoms. Patients taking warfarin *prior to* the stroke/TIA will be eligible, but INR must be  $\leq 1.5$  prior to initiation of dabigatran.

**3.3.3 Exclusion Criteria.** Patients in whom dabigatran is contraindicated according to the Canadian product monograph will not be eligible, i.e. severe renal failure or significant ongoing bleeding risk, will not be eligible. These specific contraindications in the Canadian product monograph at the time are:

- Severe renal impairment (CrCl  $< 30$  mL/min)
- Hemorrhagic manifestations, bleeding diathesis, or patients with spontaneous or pharmacological impairment of hemostasis
- Lesions at risk of clinically significant bleeding, e.g. extensive cerebral infarction (hemorrhagic or ischemic) within the last 6 months, active peptic ulcer disease with recent bleeding
- Concomitant treatment with strong P-glycoprotein (P-gp) inhibitors, i.e. oral ketoconazole
- Known hypersensitivity to dabigatran or dabigatran etexilate or to any ingredient in the formulation or component of the container

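### The declared comparison of hemorrhagic transformation by start time (within 7 days versus later) has no effect estimate or interval, and no planned table can show it

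*Combined protocol and SAP*

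**What the plan says.** The Synopsis, under Statistical Analyses, announces a group comparison: "In addition we will compare the rate of hemorrhagic transformation in patients started on dabigatran within 7 days of stroke/TIA versus those started" more than 7 days after onset. The secondary outcomes in section 5.1.2 list the same comparison twice.

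The method is given only in general terms. The Synopsis says "Descriptive statistics will be used to describe all outcomes", and section 7.1 says "The primary and secondary outcomes will be defined with descriptive statistics". Section 7.1 expresses every HT rate as a percentage of patients enrolled and names time to initiation (0-2, 3-7 and >7 days) as a secondary stratum. Section 7.2 on hypotheses reads "Not applicable. The study is hypothesis generating only".

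The table shells are in Appendices 2 to 4:

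- Appendix 2 tabulates baseline characteristics by prior VKA use and dose, with a column headed "P value (VKA naive vs. VKA".
- Appendix 3 is laid out by time from event to initiation, but holds patient characteristics only.
- Appendix 4 is the only table of outcomes. Its rows are 0-2, 3-7 and >7 days after dabigatran initiation, and its columns are prior VKA use by dose. It has no interval or difference column.

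**The concern.** Start time is the registry's central question. Sections 2.2 and 3.1 set out to show that early initiation is safe, and section 2.1 expects the results to reassure clinicians who fear HT. The contrast between early and later starters is the only explicit group-against-group outcome comparison in the plan. Carried out as written, it yields two percentages with nothing to show how far apart the underlying rates might be.

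Appendix 4, as labelled, counts days from the first dose to the event, whereas the declared comparison needs days from symptom onset to the first dose. These are different time axes. A patient started on day 10 whose HT appears 2 days later falls in the 0-2 day row of Appendix 4, but belongs to the late-start group.

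At stake is the reading of a null-looking result. If the two percentages are close, nothing planned would stop a reader from concluding that early starting is as safe as later starting, even where the data are compatible with a material excess.

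**Working it through.** **Inputs from the documents.** N = 500 (section 7.1). Start window 14 days (section 4.1), so the late group is days 8 to 14. Expected symptomatic HT rate 0.6%, derived from 1.7% under heparin and a one-third ratio (section 2.3).

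**Assumed, because the documents are silent.** The early/late split, the rate of any HT (taken as 2%, 5% and 10%), and two-sided 95% intervals. The text does not say which grade of HT the timing comparison uses, so both symptomatic and any HT are tried.

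**Step 1: the plan's own figure.** 1.7% / 3 = 0.567%, which rounds to the stated 0.6%. Expected symptomatic events: 500 x 0.006 = 3. The exact (Clopper-Pearson) 95% interval for 3/500 is 0.12% to 1.74%. N = 500 itself has no power or precision target behind it and cannot be reproduced.

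**Step 2: symptomatic HT by start time.** If all 3 expected events fell in early starters, the Newcombe 95% interval for early minus late would be:

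- 250/250 split: +1.2 points (-0.5 to +3.5)
- 400/100 split: +0.75 points (-3.0 to +2.2)

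Power to detect 1.7% early against 0.6% late is about 21% (250/250), 17% (300/200) and 6% (400/100). A test would therefore say little, and an interval is the useful output.

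**Step 3: any HT, equal observed rates.** With early rate p1 (Wilson limits l1, u1), late rate p2 (Wilson limits l2, u2) and d = p1 - p2, the Newcombe limits are:

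- lower = d - sqrt[(p1 - l1)^2 + (u2 - p2)^2]
- upper = d + sqrt[(u1 - p1)^2 + (p2 - l2)^2]

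Worked case, 20/400 versus 5/100, in percentage points. The Wilson limits are 3.26 to 7.60 and 2.15 to 11.18.

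- lower = 0 - sqrt(1.74^2 + 6.18^2) = -6.4
- upper = 0 + sqrt(2.60^2 + 2.85^2) = +3.9

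The same formula gives, for early minus late:

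| Split | 2% in both | About 5% in both | 10% in both |
|---|---|---|---|
| 250/250 | -2.8 to +2.8 | -4.0 to +4.0 (12 v 12) | -5.4 to +5.4 |
| 300/200 | -3.2 to +2.6 | -4.4 to +3.8 | -5.7 to +5.2 |
| 400/100 | -5.1 to +2.4 | -6.4 to +3.9 | -7.9 to +5.6 |

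The upper limit depends mainly on the assumed HT rate and little on the split. The lower limit widens as the late group shrinks.

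**Step 4: where could the comparison appear?** Appendix 3 has the right time axis but no outcomes. Appendix 4 has outcomes, but is labelled with the wrong axis. Neither can display HT at 7 days or less versus more than 7 days. No confidence interval is planned for any outcome; the only one in the document belongs to a cited earlier trial (section 1.1).

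**The case against.** **The study is openly descriptive.** Section 7.2 disclaims hypotheses, and a hypothesis-generating registry owes no formal test. That stands, and none is asked for here. A risk difference with an interval is itself descriptive, and the plan chose to declare a comparison.

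**The data will exist.** Section 6.2.2 has onset-to-initiation time recorded, and the strata in section 7.1 collapse to 7 days or less and more than 7 days. The row labels in Appendix 4 may be a slip, since they match those strata. Even so, relabelling would give no group totals, denominators, difference or interval.

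**Intervals are missing everywhere, including for the primary rate.** True. The gap is general, and the timing comparison is where it bears most directly on the stated aim.

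**A crude difference does not deal with confounding.** This stands. Physicians choose the start time (section 4.1), and the Limitations paragraph in section 7 accepts that patients with resolved deficits may be started earlier and that survival bias may arise. The interval shows sampling error only, and the report must say so.

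**Stronger readings about Appendix 2.** A reader might infer that its P values contradict section 7.1. They do not: the descriptive wording there covers outcomes, not baseline characteristics, and exploratory P values sit tolerably with section 7.2.

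A reader might also count the 38 variables of Appendix 1 and expect a false positive with 86% probability (1 - 0.95^38). That needs every null to be true, the tests to be independent and the whole list to be tested. The groups are not randomised, so real differences are plausible, and the variables overlap (risk scores beside their components). For the roughly 7 rows shown, the same formula gives about 30%, under the same doubtful assumptions.

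Nor do the documents establish that the INR rule "prior to initiation of dabigatran" delays prior-warfarin patients as a group. It delays only those whose INR is above 1.5 when dabigatran would otherwise start, and no INR distribution is given.

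**Conclusion.** The point holds for the timing comparison. The plan declares it, restricts it to percentages, gives no effect estimate or interval, and provides no table that can show it as labelled. With a 400/100 split and HT rates of 2%, 5% or 10%, equal observed percentages would leave open an excess in early starters of up to 2.4, 3.9 or 5.6 points. The split and the rates are assumptions, so this is a range and not a forecast.

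The documents do not say that similar rates will be reported as equal safety; that is a risk of interpretation. The Appendix 2 P values are a reporting preference and cannot change any outcome result. Overall this is a worthwhile, nearly free improvement and not a flaw in the primary analysis.

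**What to change.** In section 7.1, state that HT will be compared by time from symptom onset to dabigatran initiation (7 days or less versus more than 7 days). Name the HT grades counted, and report n/N in each group, with that group's own denominator, an exact 95% interval for each rate, and the risk difference with a 95% Newcombe interval.

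Add these rows to Appendix 4, or correct its time labels if onset-to-initiation time was intended and add the totals and difference.

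Add two sentences on interpretation: similar percentages will not be described as equal safety unless the interval supports it; and the difference is unadjusted, because physicians choose the start time.

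Optionally, replace the P-value column in Appendix 2 with standardized differences.

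The cost is plan wording, a few table rows and a little extra analysis. No new data are needed. The drawback for the sponsor is a result that may look less reassuring than two bare percentages.
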